PTSD is a major public health problem for our nations veterans. It has been estimated that up to 31% of personnel deployed to Iraq and Afghanistan, respectively, manifest symptoms of PTSD upon returning home (Sundin et al., 2010). Recent PTSD rates among active troops have been estimated at 16.7%, and even higher among reservists at 24.5% (Milliken et al., 2007). The impact of PTSD upon warriors, veterans, and their families is overwhelming. Those suffering from PTSD are at six-fold greater risk of committing suicide, and greatly increased risk of dropping out of school and having marital difficulties (Kessler, 2000). The costs to society are enormous.

Most veterans with PTSD receive a variety of treatments. There is evidence that psychotherapy, sometimes with adjunctive medication, reduces symptoms in most patients. Although the majority of patients improve, most continue to have significant residual symptoms for many years following the diagnosis (Bradley et al., 2005). There is no one treatment that is likely to totally

alleviate all symptoms of PTSD, and patients are likely to need multimodal therapy involving psychotherapy possibly augmented by pharmacotherapy in order to achieve maximal benefit (Pratchett et al., 2011). These findings highlight the need to develop additional treatment approaches that, alone or combination, may improve outcome above and beyond existing treatment methods.

9. Multi-center Study: 2 Study Sites-UCLA and VA GLA

- a) Name and FWA number of each participating institution:
 - Laboratory of Brain, Behavior and Pharmacology Semel Institute University of California, Los Angeles FWA:00004642
 - 2) VA Greater Los Angeles [name] FWA:00000734
 - a) PTSD Clinic [name]
 - b) Domiciliary Care Program [name]
- b) Contact name and information for the Investigator(s) at each participating institution:

Contact for both sites: [name]. Semel Institute at UCLA [name] P [contact] F [contact] E: [contact]

- c) Role of each participating institution (e.g., recruitment, sample/data collection, sample/data analysis, etc.):
 - VA GLA -- Identification, recruitment, and consenting of the total 74 participants at the VA GLA PTSD Clinic or Domiciliary Care Program. Week 0 (baseline), week 4 and week 8(final) visits will be performed at the VA. Additional study visits may take place at the VA GLA.

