Subjects will be followed weekly with ratings of PTSD symptoms, mood and anxiety, as well as examinations for risk of suicidality. Week 8 endpoint measures will include severity and frequency of PTSD symptoms, quality of sleep, and quality of life measures. The primary endpoint measure is the change in symptom severity at the week 8 visit. The week 8 time point will be used to compare changes in symptoms between subjects who were randomly assigned to the active vs. sham TNS treatment condition. Subjects also will be interviewed an additional 4 weeks after the conclusion of the sham controlled treatment, and their mood and anxiety symptoms assessed, to examine the durability of any symptom change that subjects experienced during the initial 8 weeks. At the end of week 8, subject improvement will be assessed and those showing a $\geq 25\%$ improvement from baseline at the end of 8 weeks of treatment will be eligible to participate in the 42-month extension phase to monitor and observe possible benefits of prolonged TNS in responders. Subjects who participate in the extension phase will remain blinded. Subjects complete the PCL-M and BDI monthly during their participation in the extension phase. The PCL-M monthly score determines on-going inclusion in this phase. Subjects will be withdrawn in the case of adverse events, or symptom worsening (quantified as > 25%worsening in symptoms after one month as compared to the beginning of the extension phase as assessed using the PCL-M total score). Subjects way also voluntarily withdraw from the extension phase at any time.

Subjects who do not participate in the extension phase will be unblinded and told whether they received the active or sham-controlled treatment after all study and follow-up visits have been completed. This includes completion of the eight-week double-blind treatment phase and four-week follow-up phase for a total of 12 weeks in this study. Data will be examined for differences

between active and sham treatment, as well as safety and acceptability of the treatment. If positive, this preliminary study will serve as the basis for a larger pivotal trial of effectiveness.

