Inquiry (SAFTEE-SI) (Levine and Schooler, 1986), an easy to use 55-item self-report (with an additional overall severity item) that rates most commonly reported side effects expected with the clinical study interventions. While developed for medication studies, it is applicable to device studies as well, and will be used to describe side effects associated with treatment. The SAFTEE-SI will be administered at enrollment and at each follow-up visit, to detect treatment-emergent events or events which worsen during treatment. The SAFTEE-SI will be supplemented by an open-ended question ("general inquiry") to capture any adverse reactions not enumerated in the SAFTEE-SI items. Events will be categorized using the Medical Dictionary for Regulatory Affairs (MedDRA), a clinically validated terminology that applies to all phases of drug and medical device development, and developed by the International Conference on Harmonisation (ICH) as a successor to the earlier COSTAR ("Coding Symbols for Thesaurus of Adverse Reaction") nomenclature.

Scales from the Deployment Risk and Resilience Inventory-2 (DRRI-2) (baseline)

This 'Trauma and Adversity Exposure' protocol includes the following four self-reported, deployment-related subscales from the Deployment Risk and Resilience Inventory-2 (DRRI-2) (Vogt et al., 2013): Difficult Living and Working Environment (14 items); Combat Experiences (17 items); Aftermath of Battle (13 items); and Perceived Threat (12 items). Items are rated on Likert-style scales and added together to give a score for each scale. See: http://www.ptsd.va.gov/PTSD/professional/assessment/deployment/index.asp

Difficult Living and Working Environment Scale (14 items) DRRI-2 Section: C; Survey Label: "Deployment Environment." This scale assesses exposure to events or circumstances representing repeated or day-to-day irritations and pressures related to life during military deployment. These personal discomforts or deprivations may include the lack of desirable food, lack of privacy, poor living arrangements, uncomfortable climate, cultural difficulties, and constraints to performing one's duties.

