Visit Type	Week 0 (Baseline)	Week 1	Week 2	Week 3	Week 4	Week 5	Week 6	Week 7	Week 8
Visit Length	*6 hrs	2 hrs	2 hrs	2 hrs	4 hrs	2 hrs	2 hrs	2 hrs	4 hrs
Questionnaire /Survey:									
MINI	Х								
CAPS-5	Х				Χ				Х
PTAQ	Х								
PCL-M	Х	Χ	Х	Х	Χ	Χ	Χ	X	Х
BDI	Х	Х	Х	Х	Χ	Χ	Χ	Х	Х
ASI	Х								Х
SF-36	Х				Х				Х
PSQI	Х	Х	Х		Х				Х
SAFTEE-SI	Х	Х	Х	Х	Х	Х	Х	Х	Х
DRRI-2 (4 scales)	Х								
LEC-5	Х			ĺ	Ì				Ì
E-TRIP	Х		ĺ	i i					İ
Treatment Blinding Questionnaire									х
Safety and Compliance		Х	Х	Х	Х	Х	Х	Х	Х
Study Procedures:									
Urine Test	Х								
Pregnancy Test (Females only)	Х								
Simulation Log Check	Х	х	Х	Х	Х	Х	Х	Х	х
Device Setting Adjustments	х				Х				

Table 1 Schedule for administration of diagnostic and rating instruments in the main study

Visit Type	Monthly	Final visit					
Visit Length	30 mins	4 hrs					
Questionnaire/Survey:							
MINI		Х					
CAPS-5		Х					
PTAQ		Х					
PCL-M	X	Х					
BDI	X	Х					
ASI		Х					
SF-36		Х					
PSQI		Х					
SAFTEE-SI		Х					
DRRI-2 (4 scales)		Х					
LEC-5		Х					
E-TRIP		Х					
Treatment Blinding Questionnaire							
Safety and Compliance	Х	Х					

Table 2: Schedule for administration of diagnostic and rating instruments in the extension phase

MINI Version 5.0: Mini International Neuropsychiatric Interview for DSM-IV

CAPS-5: Clinician-Administered PTSD Scale for DSM-V

PTAQ: Post-traumatic Amnesia Questionnaire

PCL-5: PTSD Checklist for DSM-V BDI: Beck Depression Inventory ASI: Addiction Severity Index

SF-36: 36-item Short Form Health Survey

PSOI: Pittsburgh Sleep Quality Index

SAFTEE-SI: Systematic Assessment for Treatment Emergent Events-Systematic Inquiry

LEC-5: Life Events Checklist for DSM-5, self-report

E-TRIP: Emory Treatment Resistance Interview for PTSD

Treatment Blinding Questionnaire: Survey to assess what treatment is thought to be received DRRI-2 Section C, Deployment Environment: 14-item scale assesses exposure to events or circumstances representing repeated or day-to-day irritations and pressures related to life during military deployment.

DRRI-2 Section D, Combat Experiences: 17-item scale assesses exposure to combat-related circumstances.

DRRI-2 Section E, Postbattle Experiences: 13-item scale assesses exposure to the consequences of combat.

DRRI-2 Section G, Deployment Concerns: 12-item assesses fear for one's safety and well-being during deployment.

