Safety and Compliance: Assessment will be performed by the research coordinator to assure the device is being used safely and as directed.

Assessment instruments will be administered by the study coordinator ([name], R.N., [name] and [name]). [name] has over 20 years experience in assessment of psychiatric patients in clinical trials. She will undergo standardized refresher training in conducting the MINI interview, and in administering or supervising completion of the instruments utilized in this study. She will undergo training in administering the CAPS-5 through the Trauma Psychiatry Program at UCLA ([name]., Director). Training will include practice interviews and feedback from trainers designed to calibrate to a consistent acceptable standard of administration.

TNS stimulation procedure. TNS will be performed using a CE-mark approved neurostimulator, the Monarch eTNS SystemTM (NeuroSigma, Inc., Los Angeles CA); in August 2012, NeuroSigma received CE mark certification for use of the Monarch for adjunctive treatment in epilepsy and MDD in adults and children age 9 and older. The Monarch comprises two elements: the electrical pulse generator and the hypoallergenic, self-adhering custom electrodes for delivery of the signal to the supraorbital and supratrochlear branches of the V1 division of the trigeminal nerve. The system offers features not available in off-the-shelf transcutaneous nerve stimulators, such as limiting the applied current to known safe ranges and two levels of lock-out codes to prevent the device from being used by others or reprogrammed by the subject. As well, the composition and geometry of the electrodes has been engineered to provide the optimal amount of adhesion to be worn for 7-9 hours with a gel devoid of volatile compounds that are present in most surface electrodes used for nerve stimulation and that lead to skin irritation.

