Following randomization, subjects will be scheduled to come back for a second visit when they will be given a pre-programmed stimulator, a supply of electrodes, and instructions on how to apply the electrodes and use the device. No more than one week will elapse between the first and second baseline visits. Baseline measures will not be repeated at the second baseline visit except for the CAPS-5, PCL-5, and BDI measures, which will be repeated in order to have PTSD, anxiety, and depression severity measures immediately prior to the start of treatment. Subjects will return to UCLA or the VA GLA for weekly visits and will undergo assessment of symptoms with instruments as specified in Table 1 above. The research coordinator will assess compliance, ensure that the device continues to be in good working order and that the subject has a sufficient supply of electrodes, and encourage continued compliance. In addition, the research coordinator will assess the subject for safety, inquiring specifically about any suicidal ideation and evaluate the results of scheduled assessments. If the research coordinator has any concerns about subject safety, she will immediately contact a study physician who will interview the subject and perform an independent assessment. Subjects will be removed from the study and hospitalized for any safety concerns per the procedure in the Human Subjects section.

At the conclusion of the main study (week 8 visit or sooner if the subject drops out or is removed from the study), subject improvement will be assessed and those showing a \geq 25% improvement from baseline at the end of 8 weeks of treatment will be eligible to participate in the 42-month extension phase to monitor and observe possible benefits of prolonged TNS in responders. Subjects who participate in the extension phase will remain blinded and will be asked to complete the Beck Depression Inventory(BDI) and the PTSD checklist during a monthly phone visit. Subjects who do not participate in the extension phase will be unblinded and told whether they

received the active or sham-controlled treatment after all study and follow-up visits have been completed. The device will be collected from the subject and the subject will be continue treatment in the PTSD Clinic or the Domiciliary Care Program. A summary of the results for each subject in the study will be provided to the clinic staff with the subject's permission.

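### The SAFTEE-SI is scheduled weekly in the main study but only once, at the final visit, in an extension of up to 42 months, and the text and Table 2 need to be reconciled

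*Combined protocol and SAP*

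**What the plan says.** Under Screening Procedures and Instruments in section 13, the SAFTEE-SI is a 55-item self-report form with an added overall severity item, supplemented by an open-ended question. On timing the text says: "The SAFTEE-SI will be administered at enrollment and at each follow-up visit, to detect treatment-emergent events or events which worsen during treatment". The paragraph it belongs to opens by placing safety, compliance and tolerability assessment at the weekly visits, and has the coordinator examine the subject's log booklet each week for adverse events.

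Table 1 ("Schedule for administration of diagnostic and rating instruments in the main study") marks the SAFTEE-SI at all nine visits, Week 0 to Week 8, and has a row for the log check. Table 2 ("Schedule for administration of diagnostic and rating instruments in the extension phase") has a monthly and a final-visit column. The SAFTEE-SI is marked in the final-visit column only. The monthly column holds the PTSD checklist (shown as PCL-M), the BDI and the Safety and Compliance row. There is no log-check row.

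The text agrees with Table 2 on the monthly scales: under Conduct of the study, extension subjects "will be asked to complete the Beck Depression Inventory(BDI) and the PTSD checklist during a monthly phone visit". The legend after the tables explains the Safety and Compliance row as: "Assessment will be performed by the research coordinator to assure the device is being used safely and as directed". The Overview sets the extension's exit rule: "Subjects will be withdrawn in the case of adverse events, or symptom worsening".

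For the weekly visits, Conduct of the study also has the coordinator assess safety, "inquiring specifically about any suicidal ideation". It does not say whether this continues in the extension.

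**The concern.** The extension is the only part of the trial with prolonged device use, and it is where the structured adverse-event form is given least often. The withdrawal rule there depends on adverse events being known, yet between extension entry and the final visit no scheduled item is stated to elicit them. On the schedule as written, detection in that interval would rest on volunteered reports and on whatever the coordinator asks within the Safety and Compliance check. A single form at the end also relies on recall over a long interval, and a subject who leaves without a final visit would contribute no extension SAFTEE-SI data. Event frequencies gathered once, after months, cannot be set beside frequencies gathered weekly.

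There is also an asymmetry. Subjects who do not enter the extension repeat all the Week 8 instruments four weeks later, partly to see whether adverse events have resolved. Subjects still using the device at that time have no SAFTEE-SI scheduled.

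**Working it through.** The plan gives no figure to reproduce. The check is a reading of the two tables against the text, followed by a count of administrations per unit of exposure.

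**Inputs**
- Main-study treatment: 8 weeks (section 10).
- Nightly use: about 8 hours (section 13, TNS stimulation procedure). The extension text does not restate it, so 8 hours there is an assumption.
- Extension: up to 42 months, with monthly contacts (section 13, Overview and Conduct of the study).
- SAFTEE-SI marks: nine in Table 1, of which Week 0 precedes treatment, leaving eight; one in Table 2.

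**Exposure**
- Main study: 8 × 7 = 56 nights; 56 × 8 h = 448 device-hours.
- Extension, full length: 42 × 365.25/12 = 1,278 nights, or 1,278/7 = 182.6 weeks; 1,278 × 8 h = 10,224 device-hours.
- Ratio: 182.6/8 = 22.8.
- If a subject stays 12 months (an assumption; the plan gives no expected stay): 365/56 = 6.5.

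**SAFTEE-SI frequency during or after treatment**

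| Period | Administrations | Length | Frequency |
|---|---|---|---|
| Main study, after baseline | 8 | 8 weeks | 1 per week |
| Four-week follow-up (no extension) | 1 | 4 weeks | 1 per 4 weeks |
| Extension, 12-month stay | 1 | 52.1 weeks | 1 per 52.1 weeks |
| Extension, 42 months | 1 | 182.6 weeks | 1 per 182.6 weeks |

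The extension rows assume that the subject attends a final visit. Applied literally to each monthly contact, the sentence in section 13 would give about 42 administrations over a full extension (43 if the final visit is separate from the month-42 call), against one in Table 2.

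**Contradiction or gap?**
- *Broad reading.* Conduct of the study itself calls the monthly contact a visit, Table 2 lists it under visit type, and the SAFTEE-SI is kept in the extension. Each follow-up visit then includes the monthly contacts, and Table 2 contradicts the text.
- *Narrow reading.* The paragraph opens with the weekly visits. Each follow-up visit then means those, Table 1 complies, and the text says nothing about the extension.

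The phrase is not defined, so the documents do not settle which is meant. The schedule that results is the same under both. The blank cell is unlikely to be a table-reading error, because the Overview and Conduct of the study independently name only the PTSD checklist and the BDI for the monthly contact.

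**The case against.** The strongest reply is that Table 2 is a deliberately lighter schedule for a phone contact, and that safety in the extension rests on more than one form. Much of this stands. The monthly Safety and Compliance check, PTSD checklist and BDI remain. The risk-management text in section 18 has subjects reminded at each visit that their clinician is available for suicidality or adverse events, has clinic staff contacted over any safety concern, keeps physicians on call at all hours, and tells subjects to contact the study physician about adverse events. A medical monitor can stop the study, a Safety Monitoring Committee meets at least every six months, and all subjects remain regular clinic or Domiciliary patients. These provisions do not, however, schedule the structured inquiry that section 13 describes.

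A reader might go further and infer that suicidality goes unmonitored in the extension, which would be troubling given the background statement that "Those suffering from PTSD are at six-fold greater risk of committing suicide". The documents do not support that. Table 1 has no suicidality row either, so the weekly inquiry may well be carried by the Safety and Compliance row, and that row is also marked monthly in Table 2. The legend describes the row only as a check on device use, so its scope is unclear, but unclear scope does not show that the inquiry is missing. Nor can it be said that a monthly BDI score leads to no action, since the general safety route applies to any concern about a subject's state. Part of the risk text was not available to me, which is a further reason not to argue from silence.

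A reader might also compare nine forms with one. The Week 0 form precedes treatment, so the fair count is eight. Forty-two months is a ceiling, and hours on a sham device are at 0 Hz, so the ratio describes device wear rather than stimulation. The final visit is not defined as month 42 and may already mean the exit visit. Finally, the plan states no comparison of extension and weekly adverse-event rates, so non-comparability limits what can be reported but breaks no planned analysis.

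**Conclusion.** The point holds as an inconsistency, or at least a gap, in how often adverse events are systematically elicited. Eight post-baseline SAFTEE-SI administrations are scheduled over 8 weeks, and one over an extension of up to 182.6 weeks. The exposure ratio of about 23 assumes full participation and nightly use as in the main study; at a 12-month stay it is 6.5, still with one form. The conclusion does not depend on which figure applies, nor on how the follow-up wording is read.

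The consequence is weaker and less even detection of adverse events in a phase where they are a ground for withdrawal. It is not an absence of safety monitoring, and it does not make the withdrawal rule unusable, because subjects can report events at any time. Whether the log review and the suicidal-ideation inquiry apply to the monthly contacts is an open question in the text, not a demonstrated omission. The change is worth making because it is cheap and uses an instrument already in the protocol.

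**What to change.** 1. Bring Table 2 into line with the SAFTEE-SI text in section 13 by marking the form and its open-ended question in the monthly column, and state in the text that follow-up visits include the extension contacts.
2. State that the Table 2 final visit includes early exit from the extension, so that subjects who leave before month 42 are assessed if they can be reached.
3. Reconcile the Overview, the log-booklet text, the Safety and Compliance legend, Conduct of the study and Table 2 on whether the adverse-event log review and the suicidal-ideation inquiry described for the weekly visits also apply to the monthly contacts. What the clinical rule should be is for the investigators and the safety bodies to decide; this point asks only that the passages agree.

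The cost is a protocol amendment and some added minutes on each 30-minute call, for up to about 42 calls in a subject who completes the extension. The documents give no completion time for the SAFTEE-SI, so the burden should be checked before the amendment. The form is self-report, as are the PTSD checklist and BDI already collected at these calls, so no new instrument or visit is needed.

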This is a collaboration between the VA GLA and UCLA. All study activites will will be performed at the VA Greater Los Angeles or UCLA as determined by the Principal Investigator, in consultation with the PTSD Clinic and Domiciliary Care Program directors, as well as the subject's preference. Identification, recruitment and consenting of subjects for participation will be performed at the VA GLA PTSD Clinic or the Domiciliary Care Program. The baseline visit, Week 4 visit, and Week 8 visit will be conducted at the VA GLA PTSD Clinic or Domicialiary Care program without exception. All other study activities and visits will be performed at UCLA, or at the VA GLA PTSD Clinic or Domiciliary Care Program. If subjects prefer that visits be performed at the VA, the clinic director approves such visits, and space is available in the clinic, these visits will be performed at the VA GLA PTSD Clinic or the Domiciliary Care Program. Subjects will be randomized to treatment with either active or sham TNS for a period of eight weeks. Subjects will be randomly assigned in a double-blind manner (n=37 in each group); all subjects and the research staff who interact with them will be blinded to assignment, and a separate UCLA staff member of the research team who has no contact with subjects will program the TNS device settings. Subjects assigned to the sham treatment condition will receive a TNS stimulator that will look identical to the active treatment stimulator, and will follow identical procedures for the use of this stimulator. The sham unit, however, will deliver no actual nerve stimulation (i.e., it will pulse at 0 Hz). It will be explained to all subjects that they may or may not feel any sensation while using the device and any sensations or lack there of is not indicative of which treatment they are receiving. There is no noise associated with the device. The TNS device is equipped with a lighted display which will turn on to indicate to the patient when stimulation is being administered. The display on the sham device will turn on when stimulation is given at 0 Hz to avoid the appearance of a difference between the sham and active treatment.

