Pittsburgh Sleep Quality Index (PSOI) (Buysse et al., 1989): The PSOI measures the quality and patterns of sleep. Because TNS is administered at night, this scale will be used specifically to assess the effects on sleep. It will provide a more comprehensive assessment of subjects' sleep patterns than the other scales. It can be used to differentiate "poor" from "good" sleep with seven measures: subjective quality, sleep latency, duration, habitual sleep efficiency, sleep disturbances, use of sleeping medication, and daytime dysfunction over the last month. The client self-rates each of these seven areas of sleep on a 0 to 3 Likert scale. Each area can be examined independently, and a summary score is calculated with 5 or greater indicating a "poor" sleeper. The scale has good psychometric properties. It has strong internal consistency, with Cronbach's alphas 0.80 across groups and moderate to high correlations between global and component scores (Carpenter and Andrykowski, 1998). Assessment of safety, compliance, and tolerability will be performed at the weekly subject visits. All subjects will be provided with a log booklet with space to record any treatment-emergent adverse events, how long they were able to wear the TNS system each night, and whether they encountered any problems. The research coordinator will examine this booklet each week and record any specific adverse events as well as the degree of compliance. In addition, subjects will be asked to rate tolerability of treatment-emergent adverse events by completing the Systematic Assessment for Treatment Emergent Events-Specific

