The stimulators are the same device for the active and sham treatment conditions; the only differences are the frequency at which the device is set to deliver stimulation, the pulse width, and the duty cycle. The programming will be set at the UCLA site prior to the baseline visit and the week 4 visit by a member of research staff who has no contact with subjects to deliver TNS in a double-blind manner at one of two frequencies of stimulation, active (120 Hz) or sham (0 Hz); these are the active and sham stimulation conditions previously described in epilepsy studies (DeGiorgio et al., 2003; 2006; 2009; in press) as well as in MDD (Schrader et al., 2011). Preliminary data indicate that subjects report comparable perceptions of being stimulated in the two stimulation conditions. Once the device is programmed, the user will not be able to change the stimulation parameters. Current can be adjusted within a narrow range for the comfort of the subject. Preliminary data (reviewed above) indicate that in the treatment of epilepsy, a 120 Hz stimulation frequency had a significantly greater effect than 2 Hz on mood under double-blind treatment conditions. In both conditions, the current will be adjusted to maintain comfortable but perceptible levels of stimulation. TNS will be performed for approximately 8 hours each night, a protocol that subjects found acceptable in the pilot work.

Conduct of the study. After subjects are consented and qualify to enter the study, the full assessment of symptoms will be performed. The estimated time for all these procedures at the baseline visit is approximately 3 hours.

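### The rule that current be set to a perceptible level in both arms cannot be met by a 0 Hz sham, and trying to follow it could weaken the blind

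*Combined protocol and SAP*

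**What the plan says.** All of the relevant text is in Section 13 of the combined protocol and SAP.

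- **Sham output (Overview).** "The sham unit, however, will deliver no actual nerve stimulation (i.e., it will pulse at 0 Hz". The TNS stimulation procedure gives the two programmed frequencies as 120 Hz (active) and 0 Hz (sham). It says that the arms otherwise differ only in pulse width and duty cycle.
- **Current rule (TNS stimulation procedure).** "In both conditions, the current will be adjusted to maintain comfortable but perceptible levels of stimulation". A little earlier: "Current can be adjusted within a narrow range for the comfort of the subject". Neither sentence says who makes the adjustment.
- **Programming (same place).** "The programming will be set at the UCLA site prior to the baseline visit and the week 4 visit", by a staff member who does not meet subjects.
- **Blinding (Overview).** "all subjects and the research staff who interact with them will be blinded to assignment". Subjects are told that they may or may not feel something, and that "any sensations or lack there of is not indicative of which treatment they are receiving". The units look identical, make no noise, and both light their display.
- **Perception (TNS stimulation procedure).** "Preliminary data indicate that subjects report comparable perceptions of being stimulated in the two stimulation conditions". No figures follow.
- **Blinding check (Table 1).** The Treatment Blinding Questionnaire is scheduled at week 8 only.

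**The concern.** The current rule and the description of the sham cannot both be carried out. The rule sets a task whose success depends on sensation. With real pulses the task can be completed. With none it cannot. The rule also undercuts the script: a protocol that calls absence of sensation uninformative should not also require that a sensation be reached.

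At stake is the week-8 comparison of change in symptom severity. The CAPS-5 is an interview and the PTSD checklist and BDI are self-reports, so a belief about assignment, held by the subject or the rater, can move the scores. A clue that appears when the current is set would come before all the post-baseline ratings. The baseline itself is protected, because the CAPS-5, PTSD checklist and BDI are repeated just before treatment starts (Conduct of the study).

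**Working it through.** The plan gives no figure to reproduce here. The check is to set the statements side by side.

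1. **Can the rule be met in the sham arm?** Pulses delivered = frequency × time. In the sham arm this is 0 × time = 0, whatever the current. In the active arm it is 120 per second while the device is pulsing. Current sets the strength of a pulse, so with no pulses there is no strength to raise to a perceptible level. Pulse width and duty cycle also differ between arms, but neither can create a pulse at 0 Hz, and the text describes no other source of sensation in the sham. The rule can therefore be met in the active arm and not in the sham arm.

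2. **Does other text reconcile the two statements?** No. The Overview script covers what subjects are told about sensation. The sentence allowing adjustment for comfort is compatible with a 0 Hz sham. Only the added requirement that stimulation be perceptible in both conditions is not.

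3. **Who would try to follow the rule?** This is not stated. Off-site programming before baseline and week 4 may be all that Table 1 means by device setting adjustments. Subjects receive a pre-programmed unit with instructions (Conduct of the study). The text does not say whether those instructions mention a perceptible level.

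4. **Could a failed attempt reach blinded staff?** Yes, by three routes. The subject's log has space for "how long they were able to wear the TNS system each night, and whether they encountered any problems", and the research coordinator reads it weekly. The coordinator also checks that the device is used as directed, and that it still works. The study coordinator administers the rating instruments. A subject's remark that nothing can be felt could therefore reach a rater, if the same person fills these roles.

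5. **Does the statement of comparable perceptions settle it?** It points the other way from the concern but carries no data. The protocol says that the 120 Hz and 0 Hz conditions were used in earlier epilepsy and depression work, yet the one comparison whose result it reports beside this is 120 Hz against 2 Hz, and 2 Hz does pulse. Section 16 (Medical Devices) describes the PTSD pilot as open-label and says that the sham has not been tested in PTSD.

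6. **When would a problem be seen?** The questionnaire is marked at 1 of the 9 visit columns in Table 1. The follow-up four weeks later repeats all the week-8 instruments in subjects who do not enter the extension phase. Read literally, that includes the questionnaire, and these subjects are not yet unblinded. Both occasions fall after treatment, when guesses may also reflect improvement.

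**The case against.** The strongest reply is that the conflict is one of wording, and that the cue is inferred. The rule is in the passive voice and names no actor. Nothing in the documents shows that subjects are told stimulation must be felt; the only subject-facing text on sensation says the opposite. That stands: the documents support a possible cue, not an actual one.

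A second reply is that if 120 Hz is felt and 0 Hz is not, the arms differ in sensation whatever the current rule says. The main exposure would then come from the choice of an inert sham, which the Overview states openly and mitigates with identical units, no noise, a lit display, a script and a programmer without subject contact. That also stands, and it limits what a change of wording can achieve.

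Neither reply makes the rule workable in the sham arm or reconciles it with the script.

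A reader might go further and infer that the sham arm will be unblinded, or that blinded staff will titrate current and see the difference. The documents do not support either inference. They give no perception or guess rates, they assert comparable perceptions, and they do not say who adjusts current. Nor do they say that the perceptibility sentence was carried over from a 2 Hz sham, though that might be guessed.

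**Conclusion.** The contradiction is certain and lies in the current text: the plan requires perceptible stimulation in an arm that receives none. The consequence is a plausible added risk to the blind, not a demonstrated failure. It depends on two things that the documents leave open: that subjects or contact staff try to follow the rule, and that a 0 Hz unit is not felt. No effect on the treatment comparison can be calculated, and none is claimed. It would also be wrong to conclude that blinding is checked only once, given the four-week follow-up. The wording should be changed, because the remedy is cheap and the sentence works against protections that the protocol otherwise sets up with care.

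**What to change.** 1. Delete the requirement that stimulation be perceptible in both conditions.
2. Replace it with one written current-setting procedure, identical in both arms and guided by comfort only. For example, use the same fixed upward steps within the narrow range, stopping at discomfort or at a common cap, without asking whether anything is felt. Say who performs it. The documents give no current values, so the investigators must choose the steps and the cap.
3. Judge whether the unit works by its lit display, not by sensation. Keep the script in the Overview.
4. Optional: also give the existing Treatment Blinding Questionnaire at the week-1 visit and report guesses by arm descriptively. Guesses at that point are less likely than week-8 guesses to reflect improvement.

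The cost is protocol wording and one short procedure, plus one existing form at an existing visit if the option is taken. There are four drawbacks. Active subjects may still feel stimulation when sham subjects do not, so only the cue created by this rule is removed. Stops for discomfort will be rarer in the sham arm. The active current may move slightly from a perceptible level towards the highest comfortable one, which is how the open-label PTSD pilot set it (Section 16). Asking for guesses early may draw attention to sensation.
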